A series of physiologic and clinical/health outcomes will be assessed before, during and after the bed rest intervention period and recovery period:

1) Morning resting fasted variables: blood pressure; blood glucose and lipids. 2) Physical Examination, Resting EKG, Urine collection (for urinalysis, BUN, creatinine). 3) Cardiorespiratory fitness (VO₂peak) determined via a graded cycle ergometry test. 4) Body composition by; DXA scan - bone mineral density, total and partitioned lean mass, estimated visceral fat; and MRI – left and right leg mid-thigh muscle, bone and fat volume and area. 5) Muscle strength and power: Quadriceps muscle performance testing (maximal strength and power)

will be performed using a Biodex dynamometer. 6)Physical function: The Short physical performance battery (SPPB) will be used to measure lower extremity performance as a secondary outcome. 7) MRS: Mitochondrial energetic capacity (ATP_{max}) will be determined by ³¹P MRS with a brief (24 sec) bout of isometric exercise protocol. 8) Hyperinsulinemic euglycemic clamp to determine insulin sensitivity.

Participants will enter a 10-day strictly controlled bed rest intervention at the Translational Research Institute (TRI) clinical research unit and a progressive 4-week aerobic and resistance training recovery program at the exercise training facility at the TRI, if not randomized to the ambulatory recovery group. Both groups can also receive additional optional resistance exercise training following 4 weeks of the ambulatory or exercise recovery phase. Blood and skeletal muscle biopsies will be collected immediately following days 10 of the bed rest period and after 1, 2, 3 and 4 weeks of the recovery period. Adipose tissue biopsies will also be collected on bed rest day one, immediately following 10 days of bed rest, and after 4 weeks of recovery if the participant elects to do this. The adipose biopsy is available to be chosen by the participant but not required.

Background Information and Scientific Rationale

Premise: **Skeletal muscle atrophy is a clinically significant problem that occurs during disuse or immobilization** due to hospitalization, illness and injury, and leads to a loss of muscle strength and physical function (28, 42, 66). This is a particular public health problem for older adults who comprise the majority of hospital patients in the US (26, 38) and who may lose more muscle mass during bed rest (64, 88).

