Subjects who are not yet adults (infants, children, teenagers)

We are not enrolling participants who are not yet adults.

Cognitively Impaired Adults

We will not enroll cognitively impaired adults.

Adults Unable to Consent

We will not enroll adults who are unable to provide consent.

Documentation of Informed Consent Process

Documentation of the informed consent process is required to establish that the subject was accurately and adequately informed and that no study-related procedures were initiated prior to obtaining informed consent. A research team member will note in the source documentation the consent process, date consent was obtained, and that consent was obtained prior to initiating any research procedures. In the scenario of Remote Informed Consent Process documentation of all actions will be maintained as described in the

Investigator Guidance: Remote Inform Consent Process in Non-Except Research (HRP-831).

Waiver of Written Documentation of Consent or Waiver of Consent

N/A

Randomization

A randomization schedule containing the subject treatment group assignment (EX or CON) will be generated by the study statistician. A permuted blocks approach will be used with subjects stratified by gender. We will use blocks of random sizes of 4 to reach the total sample size of 20 to start (18 completers) in each group.

Study Visits

All study visits will be conducted at the AdventHealth Translational Research Institute.

[figure not shown]

Figure 1: Schematic depiction of the study protocol.

Phase	Description	Duration	Subject at home	Subject Ambulatory	Visit Window
I	Screening	< 35 days	Yes	Yes	35 days within PBR1
II	Pre-Bed Rest	5 days	Yes	Yes	-
III	Bed Rest	10 days	No	No	-
IV	Ambulatory/Exercise Recovery	4 weeks	Yes	Yes	\pm 1 days
V	Optional Resistance Exercise	4 weeks	Yes	Yes	\pm 2 days

Phase I – Screening.

Screening Visit 1

Approximate visit time: ~ 4 hours

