Capillary blood glucose will be measured four times a day for type 2 diabetics, before each meal and at bedtime. If two consecutive results of $> 240\text{mg/dl}$ are recorded, the study physician will review and change the patient's current treatment regimen (DPP-4 inhibitors, sulfonylureas and/or Metformin) to prevent further hyperglycemia. If two consecutive results of $> 270\text{mg/dl}$ are recorded, the study physician may initiate insulin therapy. Insulin therapy will continue until the participant reaches a target glucose range of 140–180 mg/dL (7.8–10.0 mmol/L). The participant's treatment regimen and diet will be reviewed and changed as necessary to prevent hypoglycemia ($< 70\text{ mg/dL}$), although this is not expected with medications like, DPP-4 inhibitors and/or Metformin.

The following table summarizes the schedule of assessment during Bed Rest.

Assessment	Bed Rest (Days)										
	1	2	3	4	5	6	7	8	9	10	11 (post BR)
Placement of Accelerometers	X	X	X	X	X	X	X	X	X	X	X
Adverse events	X	X	X	X	X	X	X	X	X	X	X
Medication/supplement history	X	X	X	X	X	X	X	X	X	X	
Eucaloric Diet - Adequate protein	X	X	X	X	X	X	X	X	X	X	
Vital signs	X	X	X	X	X	X	X	X	X	X	X
Passive Exercise⁴	X	X	X	X	X	X	X	X	X	X	
Incentive spirometer⁵	X	X	X	X	X	X	X	X	X	X	
Evaluate DVT risk	X	X	X	X	X	X	X	X	X	X	
Body Weight	X		X		X		X		X	X	
Metabolic Body Weight¹⁶											X
Glucose Clamp - 4Hr⁶											X
RMR¹⁰											X
24-Hour Urine											X
Blood draw (hemoglobin and hematocrit)⁷							X				X
Deuterated H₂O administration⁸										X	X
Fasting Muscle Biopsy/Blood draw¹											X
Fasting Adipose Biopsy² (optional)	X									X	
Anticoagulant Therapy		X	X	X	X	X	X	X	X		

DEXA³								X	
MR Assessments (ATPmax/IMCL/IMAT³)								X	
Orthostatic Hypotension Assessment¹¹								X	
VO₂max test									X
400m walk test									X
BiodeX/Strength testing								X	
SPPB								X	
Step Test								X	
Questionnaires⁹									X

¹Muscle Tissue Biopsy: For this study fasted is defined as consuming no food (except for water and allowed medications/dietary supplements) for at least 8 hours the before blood draw/muscle biopsy. Fasting status should be verified verbally with the subject. A venipuncture blood draw will also be taken prior to each muscle biopsy (Approximately 44ml on Day 10)). Blood will be processed, aliquoted and stored at -80C.

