Our group has performed more than 1,500 muscle biopsies during the past 20 years (600 during the past 4 years since the move to the TRI), including same day serial biopsy studies and studies in men and women over 90 years old (14, 17-19, 34, 35). We will conduct 1 biopsy immediately post bed rest (day 10) and 4 biopsies of the vastus lateralis during the ambulatory or exercise recovery interventions. The approximate locations of the biopsies will be balanced as indicated to avoid interference from previous muscle biopsies (See Figure). A biopsy of the Vastus Lateralis muscle will be performed using the Bergstrom technique. Subjects will be placed in a supine position and the skin will be cleansed with chlorhexidine solution. After a sterile drape is placed over the skin, local anesthesia will be administered using lidocaine. The skin will be incised (approximately 0.5 cm) with a #11 scalpel, and the Bergstrom needle will be inserted into the Vastus Lateralis. Approximately 150 mg of muscle tissue will be obtained under suction. After the biopsy, pressure will be applied to stop bleeding and the skin will be closed with steri-strips (suture(s) if allergy to steri-strips). A sterile dressing will be applied. An MD, DO, NP, or PA will conduct this procedure. This procedure is well-tolerated in older adults. Subjects will not perform physical exercise 48 hours prior to the muscle biopsy to help prevent acute effects of exercise on muscle lipid and the other primary outcomes. Muscle specimens will be trimmed of any visible adipose and connective tissue using a dissecting microscope and processed. The following assays will be performed on the muscle biopsy specimens:

1. Mitochondrial respiration will be measured in permeabilized muscle fibers from vastus lateralis biopsies using the Oxygraph 2K system (Oroboros, Innsbruck, Austria). This approach permits a comprehensive evaluation of mitochondrial respiratory function upon titration with ETC complex-specific

inhibitors and substrates (56). We assess complex I+II supported respiration and palmitate β -oxidation supported respiration in separate assay protocols. Submaximal and maximal, coupled and uncoupled respiration will be evaluated along with coupling control ratios. This technique is well established in our laboratory (16, 19, 35) and we have conducted respirometry assays in over 500 muscle biopsy specimens in recent years.

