will be performed using an automated software program. This powerful approach will enable us to analyze over 30 lipid classes and hundreds to thousands of individual lipid species collectively representing more than 95% of the total content of the lipidome in human muscle. Total content and individual species of sphingolipid will be quantified. Cardiolipin will be quantified as an index of mitochondrial content as will oxidatively modified phospholipids malondialdehyde and 4-hydroxy-2,3-trans-nonenal.

6. Immunoblot for activation of protein synthesis/degradation pathways. Key mediators of protein synthesis (AKT/P-AKT, P-mTORC2, P-4EBP, P-eIF4B P-S6K, P-S6), autophagy/proteasome mediated breakdown (P-FOXO3a, MuRF-1, Atrogin-1, LC3B1/2, Beclin-1, p62), and mitochondria content (OXPHOS) among others will be quantified by immunoblot with validated antibodies and +/- controls. This is a standard assay that is routinely performed in our group.
7. Histochemical analysis for fiber type and muscle lipid will be determined by Oil red O staining intensity and cross-sectional area will be determined in type I and type II myocytes performed on serial sections using a modified version of methods previously used in our laboratory (14, 17). Other histological staining may also be performed, including but not limited to SDH and Glycogen.

²Adipose Tissue Biopsy: This is an optional procedure that the participant will consent to if they would like to have it done. After vital signs are obtained, subjects will be placed in a supine position. The abdominal skin 6-10 cm lateral to the umbilicus will be cleansed with chlorhexidine. A sterile drape is placed, and the skin and adipose tissue will be anesthetized using Tumescent lidocaine. Depending on adipose deposits available and the clinician's judgment, either a 3-4 mm Mercedes Liposuction needle, 13g Yale needle, or a 4-6 mm Bergstrom needle will be inserted for aspiration of approximately 1000 mg of adipose tissue. Once the sample is aspirated, the needle will be removed. In the instance where the use of a needle under aspiration yields inadequate amounts of adipose tissue, additional adipose tissue may be collected using forceps and a scalpel to excise visible superficially located subcutaneous adipose tissue. The incision will be closed with steri-strips (suture(s) if allergy to steri-strips), and sterile dressing will be applied. An MD, DO, NP, or PA will conduct this procedure.

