³Imaging Assessments (DEXA, IMAT, ATPmax and IMCL) previously defined in PreBed Rest Phase.

⁴We will mitigate risk of VTE with daily passive exercise and through prophylactic anticoagulation with low-molecular weight heparin. Daily passive exercise will be given throughout bed rest. Low-molecular weight heparin will be given throughout bed rest, except on days when patient will undergo biopsy.

⁵Participants will be instructed to use an incentive spirometer 5-10 times per day (every 1-2 hours) during bedrest to help clear their lungs.

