According to the ACCP, the Padua Risk Prediction score provides the best available model for assessing risk – based on the Padua Risk Prediction model, [which assigns 3 points to reduced mobility, 1 point to Age ≥ 70 , and 1 point to Obesity (BMI ≥ 30)] the majority of participants in this study will have a score ≥ 4 , which qualifies as “high risk of VTE”. We will mitigate risk of VTE in our participants by employing a comprehensive prophylactic plan that includes anticoagulation with low-molecular weight heparin and daily passive exercise throughout bed rest.

Non-treated baseline risk of bleeding was defined as 0.4% based on the control arm of trials of thromboprophylaxis in medical patients. Subsequent analysis of any anticoagulant vs. none to prevent VTE and low-molecular weight heparin (LMWH) vs. low-dose unfractionated heparin (LDUH) demonstrate a significant reduction in fatal pulmonary embolisms (PEs) and a reduction in symptomatic deep venous thrombosis (DVT). The effect of anticoagulation on major bleeding was not statistically significant (and relatively low, from baseline risk of 4 per 1,000 to 1 more per 1,000). There was no statistically significant effect of anticoagulation on all-cause mortality.

In addition to the risk of bleeding described above, heparin-based anticoagulation is associated with a rare entity called heparin induced thrombocytopenia (HIT). As per the ACCP Evidence Based Guidelines, medical patients who are only receiving LMWH will not have routine platelet count monitoring and the associated risk of HIT is $<0.1\%$.

Mechanical methods of thromboprophylaxis were evaluated and associated with an unfavorable rate of skin issues and less risk reduction for symptomatic DVT as compared to anticoagulation in high risk patients. Intermittent pneumatic compression devices had not been studied in hospitalized medical patients; data reviewed through a meta-analysis failed to demonstrate a beneficial effect on mortality or PE but reduced the risk of DVT primarily in surgical patients. Thus, compression devices will not be utilized.

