Therefore, we will mitigate risk of VTE in our high-risk participant population through prophylactic anticoagulation with low-molecular weight heparin given its safety profile and advantageous dosing frequency (qd vs. BID/TID for LDUH). Participants will receive enoxaparin 40mg subcutaneous injection, daily while immobile, with dose held only on the day of biopsies to minimize risk of bleeding or oozing intra- and post-procedurally. We will employ the daily passive exercise, throughout bed rest.

Every effort to prevent a study-related injury will be taken. If a DVT is suspected, the participant will be assessed by a provider, withdrawn from the study, and instructed to seek emergency treatment immediately. Sources: Prevention of VTE in Nonsurgical Patients - [https://journal.chestnet.org/article/S0012-3692\(12\)60124-X/fulltext](https://journal.chestnet.org/article/S0012-3692(12)60124-X/fulltext)

HIT - [https://journal.chestnet.org/article/S0012-3692\(15\)31496-3/pdf](https://journal.chestnet.org/article/S0012-3692(15)31496-3/pdf)

Pneumonia Prevention

Participants will also use an incentive spirometer 5-10 times (every 1-2 hours) daily to prevent pneumonia.

Glycemic management protocol. Hyperglycemia and hypoglycemia are risks for hospitalized patients with T2D and are associated with adverse health outcomes. To mitigate this risk patients with HA1C < 8.0% will be recruited. In addition, a glycemic management protocol will be administered for type 2 diabetics by the study physician. Capillary blood glucose will be measured four times a day, before each meal and at bedtime. If two consecutive results of > 240mg/dl are recorded, the study physician will review and change the patient's current treatment regimen (DPP-4 inhibitors, sulfonylureas and/or Metformin) to prevent further hyperglycemia. If two consecutive results of >270mg/dl are recorded, the study physician may initiate insulin therapy. Insulin therapy will continue until the participant reaches a target glucose range of 140–180 mg/dL (7.8–10.0 mmol/L). The participant's treatment regimen and diet will be reviewed and changed as necessary to prevent hypoglycemia (<70 mg/dL), although this is not expected with medications like, DPP-4 inhibitors and/or Metformin.

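### The bed-rest schedule starts enoxaparin on day 2 for everyone, but the text withholds it only on biopsy days, so participants who decline the optional day-1 adipose biopsy get 8 doses by the table and 9 by the text

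*Protocol*

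**What the plan says.** The dosing rule appears twice in the protocol text, in compatible terms:

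- Mitigation of Risks, Venous Thromboembolism: enoxaparin 40 mg subcutaneously, "daily while immobile, with dose held only on the day of biopsies to minimize risk of bleeding".
- Phase III, footnote 4 to the bed-rest schedule: "Low-molecular weight heparin will be given throughout bed rest, except on days when patient will undergo biopsy".

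The bed-rest schedule has a row labelled "Anticoagulant Therapy". It is marked on days 2 to 9 and blank on days 1, 10 and 11. The row carries no footnote number; footnote 4 is attached to the passive-exercise row.

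The biopsies that could trigger a hold during bed rest are these:

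- Adipose biopsy, scheduled on days 1 and 10. Footnote 2 says "This is an optional procedure that the participant will consent to if they would like to have it done", and the Introduction says "The adipose biopsy is available to be chosen by the participant but not required".
- Muscle biopsy. Footnote 1 has the words "We will conduct 1 biopsy immediately post bed rest (day 10" in parentheses and places no muscle biopsy on day 1.

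**The concern.** The text ties the hold to the individual participant's biopsy days and allows no other exception. The table fixes the hold on day 1 for everyone. Since the only day-1 biopsy is elective, the two instructions diverge for every participant who declines it.

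The stake is a safety procedure. The protocol expects the majority of participants to reach a Padua score of 4 or more, which it classes as high risk of VTE. It answers that risk with a "comprehensive prophylactic plan that includes anticoagulation with low-molecular weight heparin and daily passive exercise throughout bed rest", and it rules out compression devices. For a decliner dosed by the table, passive exercise would be the only VTE prevention on day 1, with no biopsy to justify the omission. Bed rest may also begin on the evening of the last pre-bed-rest day, so such a participant could be immobile that night and through day 1 before the first dose.

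Staff cannot satisfy both sources. Giving the day-1 dose departs from the schedule, and omitting it departs from the text.

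**Working it through.** This is a day count.

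**Inputs**

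| Input | Value | Source |
|---|---|---|
| Bed-rest days | 1 to 10 | Study Intervention Description; Phase III |
| Text rule | daily, except the participant's biopsy days | Venous Thromboembolism; footnote 4 |
| Table rule | days 2 to 9 for all | Phase III schedule, anticoagulant row |
| Muscle biopsy (all participants) | day 10 | Footnote 1 |
| Adipose biopsy (optional) | days 1 and 10 | Phase III schedule; Introduction |
| Planned starters | 2 × 20 = 40 | Randomization: "total sample size of 20 to start (18 completers) in each group" |

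**The table's figure.** The row has 11 day cells, with marks in cells 2 to 9, giving 8 doses.

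**The text's figure.** Doses = days {1, …, 10} minus the participant's biopsy days.

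- Adipose biopsy accepted: {1, …, 10} minus {1, 10} = days 2 to 9 = 8 doses. Difference from the table: 0.
- Adipose biopsy declined: {1, …, 10} minus {10} = days 1 to 9 = 9 doses. Difference from the table: 9 − 8 = 1.

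Day 10 is blank for everyone under both sources because the muscle biopsy is done that day.

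**Total across the trial.** The share who decline, *p*, is not stated, so it is taken as an assumption from 0 to 1. Doses in conflict = 40 × *p* × 1:

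- *p* = 0: 0 doses
- *p* = 0.5: 20 doses
- *p* = 1: 40 doses

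**Sensitivity to the table's layout.** As extracted, the schedule shows the muscle biopsy under day 11 although footnote 1 says day 10. Taken literally, a decliner would have no biopsy on days 1 to 10. The text would then require 10 doses against 8 in the table. The count of 9 follows the text's explicit day 10. On either reading the table is short by at least one dose for decliners.

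**The case against.** The strongest reply is that the text already settles the matter. Footnote 4 sits under the same schedule and states the rule per participant, and the Venous Thromboembolism text agrees with it. The table can be read as the rule applied to someone having every listed procedure: its blanks on days 1 and 10 coincide with the two adipose-biopsy days. On that reading the defect is a missing condition on one row. This is a plausible account of how the row arose, but it does not reconcile the sources. The row applies to all participants, and the protocol does not say that the text overrides the schedule.

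A second objection is that column positions in a table read from PDF are unreliable. The clamp, the second haemoglobin check and the muscle biopsy all appear under day 11, where the text gives day 10. That is a fair caution for the last two columns. It does not reach day 1, where the adipose-biopsy, passive-exercise and DVT-risk rows all carry a mark and the anticoagulant row does not.

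Third, bed rest may begin during day 1, so day 1 can be a partial day. This reduces the practical consequence for some participants, but the text allows a hold only for biopsies.

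Finally, the effect is small, and this stands. At most one dose per decliner is involved. Passive exercise and DVT-risk evaluation are still scheduled on day 1, and participants are under nursing supervision. The 0 to 40 total spans the whole possible range because no decline rate is given. It also rests on the 40 starters in the Randomization section; the section on sites and number of subjects gives an estimate of 75.

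**Conclusion.** The inconsistency is real. For participants who decline the optional day-1 adipose biopsy, the text requires 9 enoxaparin doses and the schedule provides 8. For those who accept, both give 8. The per-participant difference of one 40 mg dose rests on the muscle biopsy being on day 10, as footnote 1 states. The trial-wide figure of 0 to 40 doses rests on 40 starters and an unknown decline rate.

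The clinical exposure is limited to the first day of bed rest, and other precautions remain in place. Both arms share the bed-rest schedule, so the statistical analysis and the comparison between arms are not affected. It should still be corrected, because it is a contradictory dosing instruction for a population that the protocol itself describes as mostly high risk.

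**What to change.** Mark day 1 in the anticoagulant row of the bed-rest schedule and add a footnote that the day-1 dose is held only if the optional adipose biopsy is done that day. This brings the table into line with footnote 4 and the Venous Thromboembolism text.

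If a day-2 start for everyone is intended, leave the row as it is and state that start in both text places.

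The first option costs one table mark and one footnote. It adds no procedures.
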